8.2.4. Electrocardiograms

A 12-lead ECG will be performed at each timepoint specified in [Appendix 1](#). For safety monitoring purposes, the investigator must review, sign, and date all ECG tracings. Paper or electronic copies of ECG tracings will be kept as part of the patient's permanent study file at the site.

All ECGs are to be obtained before other assessments scheduled at that same time (eg, vital sign measurements, blood draws). The patient should rest in a semirecumbent or supine position for ≥ 10 minutes in the absence of environmental distractions that may induce changes in heart rate (eg, television, radio, conversation) before each ECG collection.

8.2.5. Adverse Events

AEs will be graded and recorded throughout the study according to NCI-CTCAE Version 5.0. Characterization of toxicities will include severity, duration, and time to onset.

All AEs, including SAEs, will be collected as described in Section 9.6.

8.3. Efficacy Assessment

8.3.1. Viral Load

The nasopharyngeal swab, saliva, and blood samples will be collected at the timepoints shown in [Appendix 1](#). The samples will be tested by the method of RT-qPCR in a central laboratory for the quantitative detection of nucleic acid from SARS-CoV-2.

To obtain nasopharyngeal swab samples, insert minitip swab with a flexible shaft (wire or plastic) through the nostril parallel to the palate (not upwards) until resistance is encountered or the distance is equivalent to that from the ear to the nostril of the patient, indicating contact with the nasopharynx. Swab should reach depth equal to distance from nostrils to outer opening of the ear. Gently rub and roll the swab. Leave swab in place for several seconds to absorb secretions. Slowly remove swab while rotating it. Specimens can be collected from both sides using the same swab, but it is not necessary to collect specimens from both sides if the minitip is saturated with fluid from the first collection. If a deviated septum or blockage create difficulty in obtaining the specimen from one nostril, use the same swab to obtain the specimen from the other nostril.

The process to collect saliva samples is defined in the laboratory manual.

8.3.2. WHO 8-Point Ordinal Scale

WHO 8-point ordinal scale will be used to assess clinical status of patients, at timepoints specified in [Appendix 1](#).

Descriptor	Score
No clinical or virological evidence of infection	0
No limitation of activities	1
Limitation of activities	2
Hospitalized, no oxygen therapy	3
Oxygen by mask or nasal prongs	4
Non-invasive ventilation or high-flow oxygen	5
Intubation and mechanical ventilation	6
Ventilation and additional organ support-pressors, renal replacement therapy (RRT), extracorporeal membrane oxygenation (ECMO)	7
Death	8

8.3.3. COVID-19-Related Symptoms and Disease Severity

Investigators will assess if patients have recovered from COVID-19 based on symptoms. The COVID-19-related symptoms include, but are not limited to fever, cough, diarrhea, dizziness, rhinorrhea, anosmia, dysgeusia, sore throat, abdominal pain, anorexia, and vomiting. The assessments will be performed at the timepoints specified in [Appendix 1](#).

Investigator will assess the disease severity at each visit:

Mild COVID-19

- Positive testing by standard RT-PCR assay or equivalent test
- Symptoms of mild illness with COVID-19 that could include fever, cough, sore throat, malaise, headache, muscle pain, gastrointestinal symptoms, without shortness of breath or dyspnea
- No clinical signs indicative of Moderate, Severe, or Critical Severity

Moderate COVID-19

- Positive testing by standard RT-PCR assay or equivalent testing
- Symptoms of moderate illness with COVID-19, which could include any symptom of mild illness or shortness of breath with exertion
- Clinical signs suggestive of moderate illness with COVID-19, such as respiratory rate ≥ 20 breaths per minute, saturation of oxygen (SpO_2) $> 93\%$ on room air at sea level, heart rate ≥ 90 beats per minute
- No clinical signs indicative of Severe or Critical Illness Severity

Severe COVID-19

- Positive testing by standard RT-PCR assay or an equivalent test
- Symptoms suggestive of severe systemic illness with COVID-19, which could include any symptom of moderate illness or shortness of breath at rest, or respiratory distress
- Clinical signs indicative of severe systemic illness with COVID-19, such as respiratory rate ≥ 30 per minute, heart rate ≥ 125 per minute, $SpO_2 \leq 93\%$ on room air at sea level or $PaO_2/FiO_2 < 300$

Note: For high altitude areas, PaO_2/FiO_2 ratio should be adjusted using formula:
 $PaO_2/[FiO_2 \times (\text{barometric pressure}/760)]$.

- No criteria for Critical Severity

Critical COVID-19

- Positive testing by standard RT-PCR assay or equivalent test
- Evidence of critical illness, defined by at least one of the following:
 - Respiratory failure defined based on resource utilization requiring at least one of the following:

- Endotracheal intubation and mechanical ventilation, oxygen delivered by high-flow nasal cannula (heated, humidified, oxygen delivered via reinforced nasal cannula at flow rates > 20 L/min with fraction of delivered oxygen ≥ 0.5), noninvasive positive pressure ventilation, ECMO, or clinical diagnosis of respiratory failure (ie, clinical need for one of the preceding therapies, but preceding therapies not able to be administered in setting of resource limitation)
- Shock (defined by systolic blood pressure < 90 mmHg, or diastolic blood pressure < 60 mmHg or requiring vasopressors)
- Multi-organ dysfunction/failure

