17. APPENDICES

APPENDIX 1. SCHEDULE OF ASSESSMENTS

Period	Screening ^a		Treatment		Follow-up ^b									
	Day -3 to -1	Day 1 Predose	Day 1 2-hour postdose	Day 1	Day 3	Day 5	Day 8	Day 15	Day 22	Day 29	Day 57	Day 85	Day 113/EOS Visit ^c	Day 31 Safety Follow-up Visit ^d
Visit Window (day)			±1 hour			±1	±1	±1	±2	±2	±3	±3	±7	±3
Informed consent ^e	X													
Inclusion/exclusion criteria ^f	X													
Demography/Prior medications	X													
Medical history	X													
Review SARS-CoV-2 results ^g	X													
Randomization ^h		X												
Study drug administration ⁱ				X										
Safety assessment														
Vital signs/height and weight ^j	X	X	X	X	X		X	X		X		X	X	X
Complete physical examination ^k	X													
Targeted physical examination ^l		X			X		X	X		X		X	X	X
12-lead ECG ^m	X	X	X							X		X	X	
Adverse event ⁿ	X	X	X		X		X	X		X		X	X	X
Concomitant medication	X	X	X		X		X	X		X		X	X	X
Efficacy assessment														
RT-qPCR for SARS-CoV-2 (nasopharyngeal swab)		X			X		X	X						

Period	Screening ^a	Treatment		Follow-up ^b										
		Day -3 to -1	Day 1 Predose	Day 1 2-hour postdose	Day 3	Day 5	Day 8	Day 15	Day 22	Day 29	Day 57	Day 85	Day 113/EOS Visit ^c	Day 31 Safety Follow-up Visit ^d
Visit Window (day)				±1 hour		±1	±1	±1	±2	±2	±3	±3	±7	±3
RT-qPCR for SARS-CoV-2 (saliva ^u)			X		X	X	X	X						
RT-qPCR for SARS-CoV-2 (blood)			X		X	X	X	X						
WHO 8-point ordinal scale ^o			X		X	X	X	X	X					
COVID-19-related symptoms ^p /Disease severity ^p	X		X		X	X	X	X	X					
Laboratory assessments														
Hematology ^q	X ^r				X		X	X			X			
Chemistry ^q	X ^r				X		X	X			X			
Coagulation ^q	X ^r				X		X	X			X			
Urinalysis ^q	X ^r						X				X			
Pregnancy test ^s	X ^r										X		X	
PK blood sampling														
ADA blood sampling														
SARS-CoV-2 serology sampling ^t		X												
			■		■		■	■					■	

See Appendix 2

See Appendix 2

Abbreviations: ADA, antidrug antibody; COVID-19, Coronavirus Disease 2019; ECG, electrocardiogram; EOS, End-of-Study; SARS-CoV-2, Severe Acute Respiratory Syndrome Coronavirus 2; IRIT, Interactive Response Technology; PK, pharmacokinetics; RT-PCR, reverse transcription-polymerase chain reaction; RT-qPCR, reverse transcription-quantitative polymerase chain reaction; WHO, World Health Organization.

^a If the site is able to complete all the screening procedures, randomization, and study treatment in 1 day, the screening assessments can be combined with the Day 1 assessments

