- b Telehealth/remote nurse home visits will be permitted after Day 1 visit (treatment)/discharge from the hospital if circumstances prevent visits to the clinic. Day 5, Day 22, and Day 57 visits will be performed by phone/video.
- c The EOS Visit will be conducted within 7 days after a premature study discontinuation. The Day 113 visit is the EOS Visit for patients who complete all the previously planned study visits.
- d The Safety Follow-up Visit is only for patients who prematurely discontinue the study within 30 days after study treatment. The Safety Follow-up Visit will be conducted at 30 days (\pm 3 days) after study treatment (Day 31 [\pm 3 days]). If the premature discontinuation from study occurs within 7 days prior to Day 31 (\pm 3 days), the Safety Follow-up Visit can be combined with the EOS Visit or the Day 29 visit, as appropriate.
- e Written informed consent must be obtained before performing any study-specific procedures. Consent must be obtained using the current version of the form approved by the Independent Ethics Committee (IEC)/Institutional Review Board (IRB). The consent can be obtained via remote consent if approved by local IRB.
- f Follicle-stimulating hormone (FSH) and estradiol assessments will be performed in female patients who are $<$ 55 years of age with no spontaneous menses for \geq 12 months to identify the status of no childbearing potential (refer to [Appendix 4](#)). Historical test results are allowed.
- g Positive results of SARS-Co V-2 test (RT-PCR or other tests authorized by local regulatory authorities) \leq 72 hours prior to screening are required for confirmation of eligibility.
- h Patients enrolled will be randomized via IRT to receive placebo, BGB-DXP593 5 mg/kg, BGB-DXP593 15 mg/kg, or BGB-DXP593 30 mg/kg on Day 1.
- i The dose of BGB-DXP593 will be based on the patient's actual body weight on the day of receiving the study drug (Day 1).
- j Vital signs will be monitored approximately every 15 minutes during the infusion, and then hourly till 2 hours after the infusion; the monitoring will include measurements of body temperature ($^{\circ}$ C), pulse rate, respiratory rate, saturation of oxygen (SpO₂), and blood pressure (systolic and diastolic). Pulse rate and blood pressure will be measured while the patient is in a seated or supine position after resting for 10 minutes. Height will be measured at screening only and weight will be measured at Day 1 before study drug dosing.

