Time to resolution of all COVID-19-related symptoms is defined as the days from randomization to the first day when all symptoms were resolved. Kaplan-Meier method will be used to assess the time to resolution of all COVID-19 related symptoms. The corresponding quartiles (including the median) will be reported and a two-sided 90% CI of median, if estimable, will be constructed with a generalized Brookmeyer and Crowley method for each dosing group. Patients who have died prior to experiencing the event of interest will be censored. Their follow-up length will be arbitrarily set as (data cutoff date – first patient in date). This approach is to count death as the worst possible outcome without possibility of recovery. Patients who have ongoing symptoms will be censored at the time of end of study visit or data cutoff, whichever comes first.

[figure not shown]
Kaplan-Meier method will be used to assess all-cause mortality rate at Day 29. A two-sided 90% CI of this rate, if estimable, will be constructed using the Greenwood's formula. Patients who do not die will be censored at the time of end of study visit or data cutoff, whichever comes first .

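### On the best reading of Appendix 1, COVID-19 symptoms are last scheduled at Day 22, yet the SAP carries unresolved patients as symptomatic to the end-of-study visit or data cutoff

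*Protocol*

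**What the plan says.** **Endpoint.** Time to resolution of all COVID-19-related symptoms is a secondary endpoint. SAP Section 6.4.2 says it "is defined as the days from randomization to the first day when all symptoms were resolved". It is summarized by Kaplan-Meier quartiles for each dosing group, with a 90% confidence interval for the median.

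**Collection.** Protocol Section 8.3.3 states "Investigators will assess if patients have recovered from COVID-19 based on symptoms" and continues "The assessments will be performed at the timepoints specified in" Appendix 1. The same section adds "Investigator will assess the disease severity at each visit". In Appendix 1, symptoms and severity share one row, labelled "COVID-19-related symptoms ^p /Disease severity ^p". As extracted, that row is marked at screening, Day 1 predose, and Days 3, 5, 8, 15 and 22. The cells for Days 29, 57, 85 and 113 and for the Day 31 safety visit are empty. Footnote b says "Day 5, Day 22, and Day 57 visits will be performed by phone/video".

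**Follow-up.** Protocol Section 3.1 follows patients to Day 113 and names efficacy among the purposes.

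**Censoring.** Protocol Table 5 censors a patient without the event at the last adequate event assessment. SAP Section 6.4.2 says "Patients who have ongoing symptoms will be censored at the time of end of study visit or data cutoff, whichever comes first", and SAP Table 1 gives the same date. SAP Section 8 lists no change to the planned analysis.

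**The concern.** The analysis treats symptom status as known up to the end-of-study visit or data cutoff, but the schedule appears to stop asking about symptoms at Day 22. A patient whose cough, anosmia or dysgeusia outlasts that visit has no planned occasion on which its end would be noted. Two things follow. The later part of the curve describes time when nobody was scheduled to look, and the upper quartile that the SAP promises may not be reached. Late symptom data that were never collected cannot be recovered at the analysis stage.

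**Working it through.** **1. Which column holds the last mark?** The symptom row and the visit-window row each have 14 cells, so they can be laid side by side. In the window row, Day 3 is blank, Days 5, 8 and 15 carry ±1, Days 22 and 29 carry ±2, Days 57 and 85 carry ±3, and Day 113 carries ±7. The last symptom mark falls under the first ±2, which is Day 22. The WHO scale row ends in the same cell.

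**2. How secure is that?** Not fully. The same mapping puts blood RT-qPCR on Day 5 and hematology and urinalysis on Day 57, and both are phone/video days. In favor of Day 22, the five post-baseline marks fit Days 3, 5, 8, 15 and 22. Also, no row in the first table block has a mark at Day 5 or Day 22, so those calls need some content. The main point does not depend on the exact column. Nine post-baseline visits are scheduled (Days 3, 5, 8, 15, 22, 29, 57, 85 and 113), and the row has five marks. Unless marks were lost in extraction, at least four visits have none.

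**3. Length of the gap.** 113 − 22 = 91 days. If the last mark were really at Day 29, it would be 113 − 29 = 84 days. The SAP takes the earlier of end of study and data cutoff, so 91 is roughly the maximum, before visit windows.

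**4. Third quartile.** No document gives the share u of patients still symptomatic at Day 22, so I assume 15% to 35%. I take 43 patients per arm, all assessed through Day 22. The third quartile needs the Kaplan-Meier estimate to fall to 0.25 or below.
- 32 events leave 11/43 = 0.256, which is not enough.
- 33 events leave 10/43 = 0.233, which is enough.

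Hence P(not reached by Day 22) = P(Binomial(43, 1 − u) ≤ 32).

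| Assumed u | P(third quartile not reached), per arm | 172 × u |
|---|---|---|
| 0.15 | 0.049 | 25.8 |
| 0.20 | 0.229 | 34.4 |
| 0.25 | 0.523 | 43.0 |
| 0.30 | 0.785 | 51.6 |
| 0.35 | 0.930 | 60.2 |

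**5. A second route.** Assume exponential resolution with median m days. Day 22 is 21 days after randomization, so the unresolved share is 0.5^(21/m). For m = 7, 10, 14, 21 and 28 days this is 12.5%, 23%, 35%, 50% and 60%. The third quartile falls at 2m, which is within 21 days only if m ≤ 10.5. The median falls at m, so it is observable when m ≤ 21.

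**6. What the censoring date does.** If no event is recorded after Day 22, moving the censoring date from Day 22 to Day 113 changes no step of the curve up to Day 22. It adds a plateau of up to 91 days. If a few later resolutions come to light by chance, neither date works well. Suppose 11 of 43 are unresolved at Day 22 and one resolution is noted at an unscheduled visit on Day 40. With SAP censoring the estimate falls from 11/43 to 10/43, and Day 40 becomes the third quartile although the other ten were not asked. With censoring at the last assessment, that one patient is alone at risk and the estimate falls to zero. Only systematic later assessment resolves this.

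**The case against.** The strongest reply is that a symptom horizon of about three weeks is a reasonable choice for mild to moderate acute illness after a single dose, with a Day 8 primary endpoint. Under protocol Table 5, Kaplan-Meier handles unresolved patients correctly. The endpoint is secondary and descriptive, no between-arm test is specified for it, and an upper quartile reported as not estimable is an ordinary result. The table block is visibly imperfect, and the 5% to 93% range is driven by an assumption that no document supports.

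Much of this stands. A declared horizon would be acceptable. None is declared, however, and both Section 3.1 and the SAP point to later follow-up. The column must be checked, and the probabilities only illustrate sensitivity to u.

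A reader might go further and infer that no resolution after Day 22 can ever be recorded. The documents do not support that:
- Section 8.3.3 asks for severity at every visit.
- Symptom-directed examinations are marked at Days 29, 85 and 113.
- Unscheduled visits are allowed at any time (Section 8.7).
- Adverse events are collected to the end-of-study visit.
- The event is defined by a date, and the case report form that would show whether symptom end dates are captured is not among the documents.

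These routes are not systematic for this endpoint, though. Section 9.3.1 describes adverse events in terms of new or exacerbated conditions. It does not expressly exclude COVID-19 symptoms, but it gives no assurance that a baseline symptom that merely persists would be followed to its end. Unscheduled visits happen only on request.

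**Conclusion.** The point holds as a gap in scheduled collection together with an inconsistency between passages. On the best reading of Appendix 1, subject to the PDF, symptom assessment is last scheduled at Day 22. Section 8.3.3 and SAP Section 6.4.2 both presuppose later information. Later resolution is not systematically captured, and up to about 91 unobserved days per unresolved patient may be counted as symptomatic.

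The effect is limited to the later part of the curve and the third quartile. The chance that an arm of 43 misses that quartile by Day 22 runs from 5% to 93% as the assumed unresolved share runs from 15% to 35%. The median is unaffected if at least half resolve by Day 22. The primary endpoint is not touched.

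**What to change.** 1. Check the symptom/severity row of Appendix 1 against the source PDF.
2. Mark that row at Day 29 and at the existing Day 57, 85 and 113 contacts for patients whose symptoms are unresolved, and record the date on which the last symptom ended.
3. Reconcile the severity sentence in Section 8.3.3 with Appendix 1.
4. In SAP Section 6.4.2 and Table 1, censor unresolved patients at their last symptom assessment, as protocol Table 5 already states, instead of at the end-of-study visit or data cutoff.

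The cost is a protocol amendment to one table row, a short SAP edit and a few extra questions at contacts that already take place. The downside is that later end dates rest on recall, since contacts after Day 29 are 28 days apart (57 − 29, 85 − 57, 113 − 85).

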8.4. Pharmacokinetic Assessment and Antidrug Antibody Testing

Blood will be collected to characterize the PK of BGB-DXP593 concentrations using validated immunoassays. Blood samples will be collected for characterization of ADAs. Validated screening and confirmatory assays will be employed to detect ADAs in the samples. Samples collected for analyses of blood concentration may also be used to evaluate safety or efficacy aspects related to concerns arising during or after the study.

Blood sampling for PK and ADA will be collected at the timepoints specified in [Appendix 2](#).

Refer to the laboratory manual for instructions regarding sample collection, handling, labeling, storage, and shipping of laboratory samples. The actual time of each sample collected will be captured to the nearest minute in the eCRF and recorded in the database.

8.5. Biomarkers

Peripheral blood and/or saliva samples will be collected from patients at different timepoints specified in the Schedule of Assessments ([Appendix 1](#)) to explore the association of biomarkers with the efficacy of BGB-DXP593, including but not limited to, SARS-CoV-2 mutations, serology, cytokines and gene expression signatures.

Saliva samples will be collected at various timepoints for testing SARS-CoV-2 mutations to explore the association of potential mutations on the genomic region of the virus with the efficacy of BGB-DXP593.

Blood samples will be collected from patients on Day 1 before study drug administration for measurement of SARS-CoV-2 serology levels at baseline. Additional blood samples will also be collected at various timepoints before and after study drug administration for the measurement of potential biomarkers in peripheral blood including but not limited to cytokines and gene expression levels, for the exploration of the association of these biomarkers with the efficacy of BGB-DXP593.

Shipping, storage, and handling of blood or saliva samples for the assessment of biomarkers will be managed through a central laboratory. Refer to the laboratory manual for details of sample handling and the Schedule of Assessments ([Appendix 1](#)) for sample collection timepoints.

Blood samples will be individually processed and stored as described in the laboratory manual. Coded archival samples may be used for additional medical and/or scientific research that are outside of the current study purpose and objectives (but always in compliance with applicable

law). The research may relate to the diseases that are the subject of this study, validation of new techniques/assays, and/or associated potential medicines. This may include research to help developing ways to detect, monitor, or treat the target disease of this study.

8.6. Visit Windows

A visit window of ± 1 day is allowed for visits at Day 5, Day 8, and Day 15, ± 2 days is allowed for visits at Day 22 and Day 29, ± 3 days is allowed for visits at Day 57 and Day 85, and ± 7 days is allowed for visits at Day 113 ([Appendix 1](#) and [Appendix 2](#)). All assessments will be performed on the day of the specified visit unless an acceptable time window is specified.

8.7. Unscheduled Visits

Unscheduled visits may be performed at any time at the patient's or the investigator's request. The date and reason for the unscheduled visit must be recorded in the source documentation.

If an unscheduled visit is necessary to assess toxicity, then diagnostic tests may be performed based on the investigator's assessment as appropriate, and the results of these tests should be entered on the unscheduled visit eCRF.

9. SAFETY MONITORING AND REPORTING

The investigator is responsible for the monitoring and documentation of events that meet the criteria and definition of an AE or SAE as provided in this protocol.

9.1. Risks Associated With BGB-DXP593

No clinical data are available yet and no risk associated with BGB-DXP593 has been identified. No treatment-related toxicity was noted in monkeys at weekly repeated doses up to 300 mg/kg in the 14-day repeat dose study in monkeys.

